Unless stated otherwise, missing data will not be imputed. However, if there are dates missing for AEs or medications, some intermediate steps may be taken for the determination of being treatment emergent or not. Sections below address such procedures for the handling of those dates in the relevant analyses:

Missing or Partial AE or Medication start or stop date:

For missing or partial start-dates:

- 1. If the onset date is unknown, then the date will not be imputed and will be assigned a missing value.
- 2. If the month and day are unknown, then:
 - a. If the year matches the year of the first dose date, then impute the month and day of the first dose date.
 - b. Otherwise, assign as missing.
- 3. If the day of the month is unknown, then:
 - a. If the month and year match the month and year of the first dose date, then impute the day of the first dose date.
 - b. Otherwise, assign as missing.

For partial end-dates:

- 1. If the year is unknown, then the date will not be imputed and will be assigned a missing value.
- 2. If the month is unknown, then assign as missing.
- 3. If the day is unknown, then assign the last day of the month.

Missing Pharmacokinetic (PK) Data:

Missing FT-2102 concentration data in a given profile will not be imputed. Missing samples will be reported as no sample ("NS") and excluded from analysis. The affected

profile(s) will be evaluated whether sufficient FT-2102 concentrations are available to calculate any of the planned PK parameters.

FT-2102 concentrations below the lower limit of quantitation (LLOQ) will be indicated by BLQ in the listings and will be treated as follows:

• For predose samples prior to the FT-2102 administration: Concentrations that are BLQ or missing will be assigned a numerical value of zero for the calculation of AUC. Any anomalous concentration values observed at predose will be included in the computation of AUC. If the predose concentration is greater than 5% of C_{max}, the data will be evaluated on a case-by-case basis to determine if exclusion of the affected profile is warranted.

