Adverse Events (AEs) will be summarized and recorded from the time of first dose through 28 days after the last dose of study drug, and serious adverse events from the time of informed consent to 28 days after the last dose of study drug. AEs will be coded using the MedDRA dictionary version 19.1, with verbatim terms coded by System Organ Class (SOC) and Preferred Term (PT) and graded via the CTCAE version 4.03. Sponsor coding conventions will be applied during the creation of analysis datasets. Therefore, the raw dataset may reflect a different preferred term than the ADAE data set.

A treatment-emergent AE (TEAE) is an AE that emerges after the first dose of study drug through 28 days post last dose, having been absent pretreatment, that occurred on or after the first dose of study treatment or within 28 days after the last dose, or occurred prior to the first dose and increased in grade during study treatment. If an AE has partial onset date, the imputed onset date as specified in Section VI.C will be used to define TEAE.

The causality of an AE includes related or unrelated. A treatment-related AE is defined as an AE considered "Possibly Related", "Probably Related", or "Definitely Related" to the study drug by the investigator. Missing relationship will be treated as unknown and excluded from summary of treatment-related AEs considered to be related; events reported as "Definitely Not Related", "Probably Not Related", or "Unlikely" will be considered not related.

If the AE start or stop date is still missing after implementing the rules specified in Section VI.C, the following strategy will be used to determine whether AEs with missing start or stop dates are pre-treatment or treatment-emergent:

- 1. If the start date and stop date are both missing, the most conservative approach is taken, and the AE is considered to be treatment-emergent.
- 2. If the start date is missing but the stop date is not missing and is after the day of study dose administration, then the most conservative approach is taken, and the AE is considered to be treatment-emergent.
- 3. If the start date is missing but the stop date is not missing and is on or before the day of study dose and after the date of signed informed consent, then the AE is considered to be pre-treatment (not TEAE).

The following AE summaries will be produced for both Phase 1 and 2:

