Hydraemia
Hypervolaemia
Oedema
Oedema peripheral
Weight increased
Weight (any value > 5 kg from baseline from vital signs data)

Candidate cases of DS will be identified based on patients having: any 2 or more AESI categories from the table above occurring concomitantly. Concomitant is defined for AESIs as AE start dates within 7 days of each other. Two or more AESI can comprise a DS episode. Repeat DS episodes are separated by > 14 days between the start dates of the AESIs.

The number of patients with candidate cases who have concomitant leukocytosis will be summarized. Concomitant leukocytosis is defined as having AE PT of "Leukocytosis," "Hyperleukocytosis," or "White blood cell count increased," or having laboratory results showing leukocyte count > 10 G/L within 7 days before or after AESI.

Candidate cases will be reviewed by an adjudication committee (details are contained within a separate DS Adjudication Committee charter). Committee members will review the patient cases and adjudicate which cases are DS, and the number of episodes of DS that each patient experienced. The number and percentage of patients who have a committee-adjudicated case of DS will be tabulated.

Of the cases adjudicated as having DS, the following summaries will be presented:

- The number of patients with multiple episodes of DS will be tabulated.
- The number of patients with concomitant leukocytosis will be tabulated.
- The number of patients experiencing severe and moderate DS will be tabulated. If a patient has a reported AE of differentiation syndrome, the severity will be assessed via CTCAE grade, with severe being grade 3/4/5, and moderate being grade 2. If they did not have an investigator-reported AE of differentiation syndrome, then severe is defined as experiencing more than 3 DS AESI categories concomitantly, and moderate is defined as experiencing 2 or 3 DS AESI concomitantly as per Montesinos (2009). These will be tabulated within the first 90 days post first dose, and the first 180 days post first dose.
- The number and percentage of patients reporting at least one DS AESI will be summarized by those occurring during the first 90 and 180 and days post first dose.
- The median time to onset of the DS episode (the first DS AESI for adjudicated cases) will be calculated, along with the 1st and 3rd quartiles of time to onset and the range.
- The number and percentage of patients who also had a best overall response of CR or CRh will be tabulated

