A data listing of all ECG values will also be provided, which will list the triplicate values obtained for each timepoint, as well as the derived mean value for each nominal time point.

F. Physical Examination and Pregnancy Test

Physical examination findings and data for pregnancy test will be listed in a patient data listing, but not summarized. The records of abnormal findings prior to or after the first dose of study drug from physical exam will be captured in the medical history CRF and adverse events CRF, respectively.

G. Concomitant Medications

Medications will be coded using the WHO Drug Dictionary version of September 2016, with verbatim terms coded by Anatomical Therapeutic Chemical (ATC) classification and Preferred Term (PT).

To determine whether a medication is a prior or concomitant medication, the imputed nonmissing stop date of the medication is used. If this date is on or after the start of first dosing date of study drug, the medication will be defined as concomitant medication; otherwise it will be classified as prior medication.

If the medication stop date is missing, imputation rules specified for AE stop date will be applied. If the medication date is still missing after implementing the rules, the most conservative approach is taken, and the medication is considered to be concomitant.

The concomitant medications will be summarized by ATC classification and PT. For each medication term, the numbers and percentages of patients experiencing a medication with that term. If a patient reports the occurrence of a particular medication more than once, the medication is only counted once. These will be summarized for the Safety analysis set.

Concomitant medication is defined as any medication with a start date prior to the date of the first dose of study treatment and continuing after the first dose of study treatment or with a start date between the dates of the first and last dose of study treatment. Any medication with a start date after the date of the last dose of study treatment will not be considered a concomitant medication.

A data listing of prior and concomitant medications will be provided.

H. ECOG Performance Status

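### The partial-date rules discard a known month or year before the treatment-emergent and concomitant fallbacks apply, so some AEs and drugs (probably few) are misclassified and some onsets are lost

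*SAP*

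**What the plan says.** SAP VI.C covers partial start dates in two cases. With only the year known: "If the year matches the year of the first dose date, then impute the month and day of the first dose date". With month and year known: "If the month and year match the month and year of the first dose date, then impute the day of the first dose date". In both cases the alternative is "Otherwise, assign as missing".

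For stop dates, "If the day is unknown, then assign the last day of the month", but "If the month is unknown, then assign as missing".

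SAP VIII.B uses the imputed onset to set the treatment-emergent flag. If a date is still missing, three fallbacks follow, numbered here in the SAP's order:

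- First fallback: "If the start date and stop date are both missing, the most conservative approach is taken, and the AE is considered to be treatment-emergent".
- Second fallback: start missing and stop after dosing, treatment-emergent.
- Third fallback: start missing and stop on or before dosing but after consent, pre-treatment.

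SAP VIII.G applies the AE stop-date rule to medications. "If the medication date is still missing after implementing the rules, the most conservative approach is taken", and the drug counts as concomitant. The same section also gives a second definition of a concomitant drug: one begun before first dose and continued past it, or one begun between first and last dose.

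Onset dates are used again in SAP VIII.B. Time to onset is summarized for hepatic and gallbladder events. For candidate differentiation syndrome (DS), events are counted within 90 and 180 days of first dose, and "Concomitant is defined for AESIs as AE start dates within 7 days of each other".

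**The concern.** The aim stated in SAP VI.C is to decide whether an event is treatment-emergent. A recorded month or year often settles that without any imputation, yet the rule deletes it unless it matches first dose. The fallbacks, which suit dates that are truly unknown, then decide cases that the data have already answered.

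The results conflict with the SAP's own definitions. An event that began before dosing should count only if its grade rose on treatment, and an event that began more than 28 days after last dose should not count. A drug stopped in a year before the first-dose year fails both arms of the second definition in SAP VIII.G. Separately, on-treatment events with an unknown day lose the onset that the hepatic, gallbladder and DS summaries need.

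**Working it through.** The plan gives no figure to reproduce, so the check is to apply the rules literally. The dates are assumed for illustration: consent 28 May 2019, first dose 10 June 2019, last dose 20 December 2019. Last dose + 28 days is 17 January 2020. TE means treatment-emergent.

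| Recorded | SAP result | Known part compared first |
|---|---|---|
| AE onset May 2019, ongoing | Start and stop missing: TE (fallback 1) | May ends before 10 June: pre-treatment unless worsened |
| AE onset May 2019, stop 20 June 2019 | Start missing: TE (fallback 2) | Pre-treatment unless worsened |
| AE onset May 2019, stop 5 June 2019 | Pre-treatment (fallback 3) | Pre-treatment |
| AE onset 2018 only, ongoing | TE (fallback 1) | Pre-treatment unless worsened |
| AE onset 30 May 2019, ongoing | Not TE unless worsened | Same |
| AE onset September 2019, ongoing | TE, no onset date | TE, onset known to lie in 1–30 September |
| AE onset March 2020, ongoing | TE (fallback 1) | Wholly after 17 January 2020: not TE |
| Drug stop 2012 only | Concomitant | Prior |
| Drug stop 2018 only | Concomitant | Prior |
| Drug stop March 2012 | 31 March 2012: prior | Prior |
| Drug stop 2019 only | Concomitant | Ambiguous: concomitant |
| Drug stop wholly missing | Concomitant | Concomitant |

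Four things follow.

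- **Pre-dose events.** Rows 1 and 5 differ only in whether the day was recorded, and the flag changes. Row 3 shows that fallback 3 rescues a pre-dose event whose known stop is on or before dosing and after consent, so only some such events are affected.
- **Late events.** The March 2020 onset is outside the 28-day window but is counted.
- **On-treatment events.** The September event keeps its flag and loses its date. Its month still carries information. 1 September is 20 + 31 + 31 + 1 = 83 days after first dose and 30 September is 112 days after. The event is therefore certainly inside 180 days, and only the 90-day window is in doubt.
- **Drugs.** This error comes from the stop-date line on an unknown month, not from the start-date line. A drug with a known stop month and year is classed correctly.

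**The case against.** The strongest reply is that few records can be affected and that the direction of error is deliberate. Most of the first part stands.

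- Protocol 7.2.1 collects non-serious AEs from first dose, and puts serious AEs on the AE eCRF from first dose. Pre-dose events are therefore mainly serious ones collected from consent. They can still reach the data: SAP VIII.B records serious events from consent, and Protocol 9.2.4.2 lists events with onset before study drug.
- Protocol 6.1.3 sets a screening period of 14 days, and serious events are reportable within 24 hours, so an unknown onset day in an earlier month should be uncommon.
- AE collection generally ends 28 days after last dose or at new therapy. Only AEs judged at least possibly related are reported without a time limit.
- Protocol 5.4.1 records concomitant medications from the day before first dose, and prior anti-cancer therapies are summarized separately (SAP VII.G).
- The candidate-DS analysis is for IA2 only.
- SAP VI.C does not impute missing data unless it says so. Leaving time to onset without an invented day is consistent with that.

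A reader might infer that AE incidence, the Phase 1 primary endpoint, is materially distorted. The documents do not support that: on-treatment events remain treatment-emergent, and the pre-dose and late routes are narrow. Nor do they show that DS results in the final report are affected, or that old drugs will fill the concomitant tables.

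The appeal to conservatism does not stand in full. It justifies a default for unknown dates, not for dates whose recorded part fixes the order. For DS candidates the loss of a date is not conservative, because it can remove a symptom from case finding.

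**Conclusion.** The rules as written misclassify three kinds of record: AEs known to precede dosing that are ongoing or end after it; late-reported related AEs known to start beyond the 28-day limit; and drugs with only a stop year, earlier than the first-dose year. They also leave on-treatment events with an unknown day outside the first-dose month without a usable onset for hepatic and gallbladder time to onset and, at IA2, for the DS windows.

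The size cannot be computed, because the documents give no rate of partial dates; given the collection windows it is probably small. No hypothesis test or efficacy endpoint depends on these rules. The conclusion rests on a literal reading of SAP VI.C, VIII.B and VIII.G together; no other section adds a before/after check. The correction is worth making because the answer is already in the recorded data.

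**What to change.** Add a step to SAP VI.C ahead of the fallbacks: compare the known month and year, or year alone, with first dose and with last dose + 28 days.

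- AE start wholly before first dose: pre-treatment, unless the grade increased on treatment.
- AE start wholly after last dose + 28 days: not treatment-emergent.
- Drug stop year before the first-dose year: prior.
- Known part leaves the order ambiguous, or date wholly unknown: keep the present conservative default.

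This corrects the flags without inventing dates. For time-to-onset summaries only, a flagged onset imputed within the known month may be used. Imputed days should not be allowed to satisfy the 7-day DS rule. If day 1 were imputed throughout, events on 3 and 25 September, 22 days apart, would share a date and become a false concurrence. Send such cases to the DS adjudication committee with the known month shown.

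The cost is a few lines of SAP text and matching programming. The SAP Introduction allows changes until database lock; after that, the change would be documented as a deviation in the study report.

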4 STUDY DESIGN

This Phase 1/2 study will utilize a multicenter, open-label, dose-escalation design to evaluate the safety, efficacy, PK, and PD of FT-2102 administered orally to patients with AML or MDS.

Patients will be given FT-2102 daily (QD or BID) in continuous 28-day cycles, alone or in combination with azacitidine (administered at the dose of 75 mg/m² for 7 days IV/SC per every 28-day cycle) or LDAC (administered at the dose of 20 mg BID SC for 10 days every 28-day cycle) until treatment discontinuation. The term "study drug" will refer to either FT-2102, azacitidine or cytarabine.

Patients who discontinue for reasons other than disease progression/relapse or withdrawal of consent will continue to be followed for response until progression/relapse occurs.

Patients who achieve an adequate response to study treatment and meet other criteria required to undergo hematopoietic stem cell transplantation (HSCT) may proceed to HSCT after discontinuation of study treatment and will be followed on study for disease evaluation and any new HSCT conditioning or other new antineoplastic therapies received until disease relapse, death, withdrawal of consent, lost to follow-up, or end of study.

If a patient discontinues study drug to undergo HSCT, but is then deemed ineligible for HSCT, the patient may restart study drug with Medical Monitor approval.

Patients who undergo HSCT and then have persistent/recurrent IDH1-mutant (IDH1m) positive disease may be eligible to restart treatment with FT-2102 by re-enrolling in the appropriate Phase 2 cohort with Medical Monitor approval:

• Re-enrollment into Cohort 3 if morphologic relapse/progression

Patients who relapse post-HSCT and elect not to restart FT-2102 treatment will enter the overall survival follow-up period.

[figure not shown]
Patients participating in Phase 1 may be followed for survival for up to 12 months from C1D1 or for 28 days after treatment discontinuation (whichever is longer).

Patients participating in Phase 2 may be followed for survival for up to 36 months from C1D1 or for 28 days after treatment discontinuation (whichever is longer).

As shown in Figure 1, the study is comprised of 3 stages: a Phase 1 dose-escalation stage, a Phase 1 dose-expansion stage, and a Phase 2 stage.

Figure 1 Study Design

Phase 1 – Dose Escalation and Dose Expansion

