4.4.2 Exclusion Criteria

To be eligible for entry into the study, the patient must NOT meet any of the exclusion criteria listed below:

- 1. Phase 1 Single Agent Dose-escalation/Dose-expansion Cohorts and Phase 2
 Cohorts 1, 4, 5, 7 and 8 only: Patients who have been treated with an IDH1 targeted therapy are excluded
- 2. **Phase 2 Single Agent Cohorts 1-3 and 7 only:** Patients with IDH2 mutation detection at baseline or history of IDH2m inhibitor treatment are excluded
- 3. History of prior malignancy unless disease-free for ≥ 12 months or considered surgically cured; patients with nonmelanoma skin cancers or with carcinomas in situ are eligible regardless of the time from diagnosis (including concomitant diagnoses)
- 4. Patients with symptomatic central nervous system (CNS) metastases or other tumor location (such as spinal cord compression, other compressive mass, uncontrolled painful lesion, bone fracture, etc.) necessitating an urgent therapeutic intervention, palliative care, surgery or radiation therapy
- 5. Patients with previous allogeneic HSCT, if they meet any of the following criteria: < 100 days from time of HSCT; active acute or chronic graft vs. host disease (GvHD); or receiving immunosuppressive therapy as treatment or prophylaxis against

GvHD

Note: Doses < 20 mg methylprednisolone (or its equivalent) daily are not an exclusion criterion.

- 6. Treatment with radiation therapy, major surgery (requiring general anesthesia) within one month prior to study drug dosing
- 7. Treatment with chemotherapy or small molecule anticancer therapeutic within five half-lives of the agent or within 21 days if the half-life is unknown. Patients reenrolling in Cohort 6 after relapse/progression on Cohort 1 are exempt from this washout requirement (i.e. can continue FT-2102 treatment until re-enrollment)
- 8. Treatment with an anticancer therapeutic antibody less than four weeks before first dose of study drug
- 9. Treatment with other experimental therapies or participation in another clinical trial within a period of time that is less than the cycle length or within 21 days prior to starting study drug, whichever is shorter
- 10. Patients unable to swallow oral medications, or patients with gastrointestinal conditions (e.g., malabsorption, resection, etc.) deemed by the Investigator to jeopardize intestinal absorption

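### The SAP's predose PK rule contradicts its own no-imputation rule, and is not limited to the first-dose profile that it suits

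*SAP*

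**What the plan says.** SAP Section VI.C, under missing PK data, first states: "Missing FT-2102 concentration data in a given profile will not be imputed". Missing samples are to be reported as NS and left out of the analysis.

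A list follows that is introduced as covering values below the limit of quantitation. Its first item is headed "For predose samples prior to the FT-2102 administration" and says: "Concentrations that are BLQ or missing will be assigned a numerical value of zero for the calculation of AUC". The same item includes anomalous predose values in the AUC by default. It adds that if predose exceeds 5% of Cmax, "the data will be evaluated on a case-by-case basis to determine if exclusion of the affected profile is warranted". No cycle, day or prior-exposure condition is attached.

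Protocol Section 4 sets the dosing: "Patients will be given FT-2102 daily (QD or BID) in continuous 28-day cycles". Protocol Table 4 schedules serial sampling at predose, 0.5, 1, 2, 4 and 8 h on both C1D1 and C2D1, with a next-day sample after each, for Phase 1 patients and for Phase 2 patients with Holter monitoring. Other Phase 2 patients have only a predose sample on C2D1. Table 4 labels the C1D2 sample predose, and Protocol Section 6.1.5 places it about 24 hours after the first dose.

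**The concern.** One missing predose sample receives two treatments: excluded as NS, or entered as zero. Two programmers following the same text could produce different AUCs.

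A zero substitute and a 5% carry-over check make sense before a first dose, when no drug should be present. On C2D1 they do not. The patient has been dosed through Cycle 1, and the dose-expansion washout starts only after the C2D1 dose (Protocol Section 6.1.13). A missing value there is an unobserved trough, not zero, and a trough above 5% of Cmax is the expected finding.

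At stake are the accuracy of AUC in patients with a missed predose sample, and a screen that opens nearly all C2D1 profiles to discretionary exclusion once concentrations are known, with no stated criteria. PK parameters are a secondary endpoint, and Protocol Section 9.2.5 looks for trends that suggest accumulation.

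**Working it through.** The plan gives no figure to reproduce. Sampling times come from Protocol Table 4. Assumptions, because the documents give no human half-life, absorption rate or AUC method: one-compartment oral kinetics, half-life 2 to 72 h, absorption rate ka 0.5 to 2 per h, linear trapezoid, and BID or QD dosing over 28 days.

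**Model.** With k = ln 2 / half-life, one dose gives C(t) = ka/(ka − k) × (e^(−kt) − e^(−ka·t)) in units of dose/volume. The C2D1 profile sums this over the current and all earlier doses.

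**5% screen.** With instant absorption, trough/peak is 2^(−interval/half-life). It equals 5% when half-life = interval × ln 2 / ln 20, which is 2.78 h for BID (12 h) and 5.55 h for QD (24 h). Longer half-lives exceed 5%.

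**Zero at C2D1 predose.** The first interval is 0.5 h, so the loss is ½ × 0.5 × C(predose) = 0.25 × C(predose). For a completely flat profile the loss is 0.25/8 = 3.1% of AUC0-8 and 0.25/12 = 2.1% of AUC0-12.

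**Zero at C1D2.** The last interval runs from 8 to 24 h, so the loss is ½ × 16 × C(24) = 8 × C(24). Example with half-life 12 h and ka 1.5: C(24) = 0.260 and AUC0-24 = 13.23, so the loss is 8 × 0.260 / 13.23 = 15.7%.

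Ranges over ka 0.5 to 2:

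| Assumed half-life | Predose/Cmax, BID | Predose/Cmax, QD | AUC0-8 loss, C2D1 BID | AUC0-12 loss, C2D1 BID | First-dose AUC0-24 loss, C1D2 = 0 |
|---|---|---|---|---|---|
| 2 h | 2.7–9.6% | 0.0–0.2% | 0.17–0.43% | 0.16–0.37% | 0.1–0.2% |
| 3 h | 9.4–21.2% | 0.6–1.5% | 0.49–0.85% | 0.43–0.69% | 0.7–1.1% |
| 4 h | 17.3–32.0% | 2.2–4.3% | 0.80–1.20% | 0.67–0.94% | 2.1–2.9% |
| 6 h | 31.7–47.0% | 8.0–12.4% | 1.29–1.68% | 1.02–1.25% | 6.0–7.5% |
| 12 h | 56.7–68.7% | 28.5–36.1% | 2.04–2.32% | 1.49–1.64% | 15.5–17.8% |
| 24 h | 75.3–83.0% | 53.5–60.7% | 2.53–2.70% | 1.77–1.85% | 23.6–26.2% |
| 72 h | 91.0–94.0% | 81.2–84.9% | 2.92–2.98% | 1.98–2.01% | 30.4–33.0% |

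The AUC0-12 column takes its 12 h value from the model, because Table 4 has no 12 h sample.

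**Animal figures as a plausibility check.** Monkey data in Protocol Section 1.4 (BID, Day 88) give an average-to-peak ratio of 48,400 / 24 / 3,210 = 0.63. That is a fairly flat profile. If human profiles are similar, a BID trough below 5% of Cmax is implausible.

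**The case against.** Section VI.C opens "Unless stated otherwise, missing data will not be imputed", so the predose item can be read as a specific exception. That is possible, but the PK sentence is itself unconditional, and the exception is unlabelled inside a list about values below quantitation. The reader still has to guess.

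The 5% line triggers review, not exclusion. Anomalous predose values are included by default, and SAP Section VI.I requires excluded PK data to be discussed in the study report. This stands. A reader might infer that C2D1 profiles will be discarded, but the documents support only that nearly all would be flagged, so the screen would not discriminate.

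Four other stronger readings are also not supported:

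- That trough summaries would contain false zeros. The zero applies only to AUC; elsewhere the sample stays NS.
- That AUC0-12 would fall by 6% to 18%. This requires reusing the predose value as the 12 h value, which neither document plans.
- That Cohort 6 roll-over patients are materially affected because they "can continue FT-2102 treatment until re-enrollment". PK sampling stopped at Protocol Version 7/Amendment 6 (Protocol Section 6.4), so only an earlier roll-over patient with Holter sampling could be, and the documents do not show that any exist.
- That accumulation or exposure-response results are distorted. SAP Section I defers PK and PK/PD analyses to a separate document, and SAP Section VIII.E does the same for the QTcF model. Neither is available here.

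**Conclusion.** The contradiction is plain on the text, and the missing first-dose limit is a real gap. Under the stated assumptions, essentially every BID C2D1 profile would be flagged for half-lives of 4 h or more (already 9.4% or higher at 3 h), and QD profiles from about 6 h. The AUC error from a zero at C2D1 predose is small: about 1% to 3% of AUC0-8 and at most about 2% of AUC0-12, only in patients whose sample is missing. The literal C1D2 reading is larger, about 2% to 33% of first-dose AUC0-24 for half-lives of 4 to 72 h, again only where that sample is missing. The documents give no rate of missed samples.

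That C2D1 is at or near steady state is inferred from continuous dosing; the documents do not say so. No primary endpoint, sample size or decision rule is touched. The point deserves correction because the written rule assigns a wrong value and the remedy is short.

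**What to change.** In SAP Section VI.C:

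- Limit the zero assignment (below quantitation or missing) and the 5%-of-Cmax screen to the C1D1 predose sample in patients with no FT-2102 on board, and label this as an exception to the no-imputation sentence.
- For every other sample labelled predose (C1D2, C2D1 and later), treat a missing value as missing (NS). Report the AUC only if the remaining samples allow it. Do not substitute another trough, since that would also be imputation.
- Keep quantifiable on-treatment predose values without the 5% screen. Measured values below quantitation outside C1D1 predose then fall under the existing rule for all other such values.
- Carry the same wording into the separate PK analysis document.

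The cost is about two sentences and no new data. A few AUCs may become not calculable.
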